8.5 Efficacy Analyses

8.5.1 Primary Efficacy Analysis

8.5.1.1 Hypotheses to be Tested

The primary hypotheses will compare each dose of SUVN-502 with placebo. The null and alternative hypotheses to be tested are as follows:

$$H_0: \hat{\mu}_{SUVN-502\ 50\ mg} = \hat{\mu}_{Placebo}$$

$$H_a: \hat{\mu}_{SUVN-502\ 50\ mg} \neq \hat{\mu}_{Placebo}$$

and

$$H_0: \hat{\mu}_{SUVN-502\ 100\ mg} = \hat{\mu}_{Placebo}$$

$$H_a: \hat{\mu}_{SUVN-502\ 100\ mg} \neq \hat{\mu}_{Placebo}$$

where $\hat{\mu}$ is the mean change from baseline at week 26 for the ADAS-Cog score.

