4.7.2 Primary Efficacy Endpoint- – ADAScog-11

The primary endpoint for the assessment of efficacy is the change from Baseline to Week-26 in the ADAScog-11 score.

The ADAScog-11 is a brief measure of cognition, including word recall, commands, constructional praxis, naming objects and fingers, ideational praxis, orientation, word recognition, remembering test instructions, spoken language ability, word-finding difficulty, and comprehension of spoken language.

Word Recall

The score for this item is the mean number of words not recalled on the three trials, for a maximum score of 10.

Commands

The score for this item is based on the total number of commands performed incorrectly, where the maximum score is 5. Scoring is summarized in the chart below:

0	= all commands correct
1	= 1 command incorrect
2	= 2 commands incorrect
3	= 3 commands incorrect
4	= 4 commands incorrect
5	= 5 commands incorrect

Constructional Praxis

The score for this item is based on the total number of forms drawn incorrectly, where the maximum score is 5. Scoring is summarized in the chart below:

0	= all 4 drawings correct
1	= 1 form drawn incorrectly
2	= 2 forms drawn incorrectly
3	= 3 forms drawn incorrectly
4	= 4 forms drawn incorrectly
5	= no figures drawn

Naming Objects and Fingers

The score for this item is based on the number of different objects and fingers that the subject named incorrectly. The maximum score for this item is 5 and is summarized in the chart below:

0	= 0-2 items (objects and fingers) named incorrectly
1	= 3-5 items (objects and fingers) named incorrectly

2	= 6-8 items (objects and fingers) named incorrectly
3	= 9-11 items (objects and fingers) named incorrectly
4	= 12-14 items (objects and fingers) named incorrectly
5	= 15-17 items (objects and fingers) named incorrectly

Ideational Praxis

The score for this item is based on the total number of components the subjects are not able to perform. The maximum score is 5. Scoring is summarized in the chart below:

0	= all components performed correctly
1	= failure to perform 1 component
2	= failure to perform 2 components
3	= failure to perform 3 components
4	= failure to perform 4 components
5	= failure to perform 5 components

Orientation

The score for this item is based on the total number of responses incorrect. The maximum score is eight. Scoring is summarized in the chart below:

0	= all responses correct
1	=1 response incorrect
2	=2 responses incorrect
3	=3 responses incorrect

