4	Moderately severe	= subject has difficulty more than 50% of the time
5	Severe	= one or two word utterance; fluent, but empty speech; mute

The total score for the ADAScog-11 is the sum of the above 11 items. The maximum score is 70 points. A lower score indicates a better performance.

If any item is not administered because the subject is too cognitively impaired to complete, then the subjects receives the maximum amount of points for that item. Any other reason for not administering the item on the eCRF will be left as missing. Handling of missing items in the ADAScog-11 is summarized in [Section 4.7.1.2](#).

Summary

ADAScog-11 scores will be summarized by treatment group and visit in terms of absolute values and changes from baseline, both for the observed case and LOCF analyses.

A listing of observed and change from Baseline value will be provided.

Analysis

A MMRM will be used to test the hypotheses stated in [Section 4.7.1](#) that there is no difference between SUVN-502 and placebo in the mean change from baseline at Week 26 for the ADAScog-11 score. The LS means of each treatment group, and the differences between each SUVN-502 dose group and placebo will be reported for Weeks 4, 13, and 26, along with the corresponding 95% confidence intervals and p-values.

The change from baseline score at each scheduled post-baseline visit (according to the Study Schedule) during the treatment period will be the dependent variable. The model will include the fixed effects of treatment, week, treatment-by-week interaction, and APO-E status (carrier- one allele, carrier- two alleles, and non-carrier), as well as a continuous covariates of baseline score, the baseline score-by-week interaction, age, and Baseline MMSE score. Pooled site, as defined in [Section 4.2.4](#), will be included as a random effect. Week will be considered a categorical variable with values equal to the visit numbers at which the scales were assessed. An unstructured covariance matrix will

initially be used to model the within-subject variance-covariance errors. The following SAS code will be used to perform the analyses:

```
PROC MIXED;  
CLASS treat week subjid apoe site;  
MODEL outcome = treat week treat*week base base*week apoe mmse_base age /  
          DDFM=kr;  
RANDOM site;  
REPEATED week / SUBJECT=subjid TYPE=UN;  
LSMEANS treat/ cl diff;  
RUN;
```

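### The SAS code given for the primary analysis compares arms on the average of Weeks 4, 13 and 26, not at Week 26

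*SAP*

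**What the plan says.** The text sets the primary comparison at Week 26. SAP 4.7.2 states: "The primary endpoint for the assessment of efficacy is the change from Baseline to Week-26 in the ADAScog-11 score". Its Analysis paragraph says the MMRM tests the hypothesis of "no difference between SUVN-502 and placebo in the mean change from baseline at Week 26 for the ADAScog-11 score", and the protocol's hypotheses (8.5.1.1) define the parameter in the same way: it "is the mean change from baseline at week 26 for the ADAS-Cog score". The SAP also promises by-visit output: "differences between each SUVN-502 dose group and placebo will be reported for Weeks 4, 13, and 26", with confidence intervals and p-values.

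The SAP then commits to a program: "The following SAS code will be used to perform the analyses". Week is a CLASS variable, and the model line is "MODEL outcome = treat week treat*week base base*week apoe mmse_base age". The only request for estimates is "LSMEANS treat/ cl diff". The program has no treatment-by-week LSMEANS, ESTIMATE, LSMESTIMATE or SLICE statement.

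SAP 4.7.1, where the hypotheses are set out formally, refers to the mean change from baseline without naming a week.

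**The concern.** In PROC MIXED, LS means for a main effect are averaged with equal weight over the levels of any CLASS factor crossed with it. With treatment-by-week in the model, the treatment LS means are therefore averages over the three post-baseline visits. The code and the text give different primary tests, and the SAP has no rule for which prevails.

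The p-value that decides the trial is at stake. The averaged contrast dilutes an effect that builds over 26 weeks. It can also reject on an early effect that is gone by Week 26. The mismatch may spread: SAP 4.7.3 applies the same MMRM to the secondary endpoints, and SAP 4.7.1.6 applies the same methods to the pooled-dose comparison.

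**Working it through.** **Inputs from the documents.** 179 randomized per arm, 2-point difference, SD 6, two-sided 5% level, dropout of 20% or less (Protocol 8.9, SAP 4.10); visits at Weeks 4, 13 and 26.

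**Assumptions, not in the documents.** SDs at the three visits of 6/6/6 or 4/5/6; a common between-visit correlation ρ of 0.3 to 0.7; the effect profiles below; and, for simplicity, the same 143 subjects per arm at all three visits.

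**1. The plan's own figure.** n = 2 × 6² × (1.960 + 0.842)² / 2² ≈ 141.3, so 142 per arm. Dividing by 0.8 gives 177.5, so 178 against the stated 179. With 179 × 0.8 ≈ 143 evaluable per arm, the noncentrality is 2 / (6 × √(2/143)) = 2.82 and the noncentral-t power is 80.2%. The sample-size statement reproduces, but only for a 2-point difference tested at one time point.

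**2. The contrast in the code.** For one dose against placebo, over Weeks 4, 13 and 26:

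| Request | Dose coefficients | Placebo coefficients |
|---|---|---|
| `LSMEANS treat` | 1/3, 1/3, 1/3 | −1/3, −1/3, −1/3 |
| Week 26 difference | 0, 0, 1 | 0, 0, −1 |

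These weights do not change with dropout. As a check, the SAP's fixed-effects model was fitted by GLS to one simulated trial with 20% expected dropout. The visit differences were 0.296, 1.792 and 2.418. The treatment LS-mean difference was 1.502, which is (0.296 + 1.792 + 2.418)/3.

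**3. What the averaged contrast estimates.** If a 2-point Week 26 effect grows linearly from zero, the visit effects are 2 × 4/26 = 0.31, 2 × 13/26 = 1.00 and 2.00. Their mean is 2 × (4 + 13 + 26)/(3 × 26) = 1.10. If the effect appears only at Week 26, the mean is 2/3 = 0.67.

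**4. Its standard deviation.** SD_avg = √(Σσᵢ² + 2ρ Σσᵢσⱼ)/3, the second sum being over pairs of visits.
- SDs 6/6/6, ρ = 0.5: √(108 + 108)/3 = 4.90. For ρ = 0.6 and 0.7 it is 5.14 and 5.37.
- SDs 4/5/6, ρ = 0.6: √(77 + 2 × 0.6 × 74)/3 = 4.29.

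**5. Power of the averaged test, 143 per arm.** Example: linear profile, SD 6, ρ = 0.5. The noncentrality is 1.103 / (4.90 × √(2/143)) = 1.90 and the power is 47.5%.

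| True effect at Weeks 4, 13, 26 | Averaged estimate | Rejection by averaged test, ρ 0.3–0.7, both SD patterns | Week 26 test |
|---|---|---|---|
| 0.31, 1, 2 | 1.10 | 41–72% | 80% |
| 0, 0, 2 | 0.67 | 18–33% | 80% |
| 2, 2, 2 | 2.00 | 88% to >99% | 80% |
| 2, 1, 0 | 1.00 | 35–63% | 5% (null true) |

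For the linear profile with ρ restricted to 0.5–0.7, power is 41–48% with SD 6 throughout and 55–62% with SDs 4/5/6. For the 2, 1, 0 profile with SDs 4/5/6 and ρ = 0.6, rejection is 50%.

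**The case against.** The strongest reply is that the text already fixes the contrast. Week 26 is named in the protocol and in the paragraphs just before the code. By-visit differences and a plot of LS means over time are also required, and the quoted line can produce neither. A programmer following the SAP would have to add the interaction LS means, so this may be no more than an incomplete code fragment. That stands in part: the declared endpoint has not changed, and the losses above arise only if the p-value is taken from the code as written. But the SAP presents the code as what will be used, not as an example, and SAP 4.2 requires analyses to follow the SAP.

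Spread to other analyses is likewise an inference. SAP 4.7.3 reuses the model and itself asks for results at each week, and SAP 4.7.1.6 reuses the methods. Neither section gives its own contrast statement, so both depend on how this one is resolved.

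The magnitudes are illustrations. The documents give no visit correlations, early-visit SDs or effect profile, and for a symptomatic drug a roughly constant effect is possible, in which case the averaged test has more power. The calculation also drops the Week 4 and 13 data of dropouts, which the MMRM would keep. Assuming 18 per arm lost after Week 4 and 18 after Week 13, with SD 6 and ρ of 0.5–0.7, linear-profile power is about 48–55% for the averaged test and 83–85% at Week 26. The 50% false-success figure rises to about 57%. The levels move, but the gap remains.

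**Conclusion.** The concern holds. As written, the code tests the equal-weight average of Weeks 4, 13 and 26. The protocol and the SAP text require the Week 26 difference, for which the 80% power was calculated. This finding rests only on the model and LSMEANS lines, not on any assumed quantity. The two tests target the same quantity only if the effect averaged over the three visits happens to equal the Week 26 effect, as it does when the effect is constant.

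The size of the consequence is conditional on the assumed profile, SDs and correlation, and on the code being run unchanged. It ranges from a loss of about half the power, through a gain under a constant effect, to frequent rejection when there is no Week 26 effect. Because the plan supports two different primary p-values, this must be settled before unblinding.

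**What to change.** In SAP 4.7.2, replace the line with `LSMEANS treat*week / cl diff;`, or add an explicit Week 26 LSMESTIMATE or ESTIMATE for each dose against placebo. The interaction request prints every pairwise difference among 3 × 3 = 9 cells, 36 in all. The SAP should therefore state that the primary tests are the two Week 26 differences, 50 mg against placebo and 100 mg against placebo, and that the Week 4 and 13 differences are secondary. Add Week 26 to the primary parameter definition in SAP 4.7.1, and apply the same contrast specification in SAP 4.7.1.6 and 4.7.3. If the three-visit average is of interest, label it as supplementary.

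The cost is one line of code and a few words of text. Data collection, sample size and endpoint do not change, and SAP 4.11 allows planned analyses to be revised before database lock.

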If the unstructured covariance structure matrix results in a lack of convergence, the following covariance structures will be used in sequence: heterogeneous compound symmetry covariance structure and compound symmetry covariance structure, until the model converges. The Kenward-Roger approximation will be used to estimate the denominator degrees of freedom.

A plot showing the LS mean change from baseline in ADAScog-11 over time within each treatment group will be provided.

Sensitivity analyses to investigate the impact of the choice of method for handling missing data and the choice of analysis population will be performed as described in [Section 4.7.1.2](#).

The homogeneity of the treatment effect for a number of important subgroups will be investigated as described in [Section 4.7.1.5](#).

The combined treatment effect of SUVN-502 regardless of dose will be investigated as described in [Section 4.7.1.6](#).

Additional ADAScog-11 analyses will be performed on subsets of the mITT Population and EP:

- [REDACTED]
- [REDACTED]
- [REDACTED]

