4.10 Determination of Sample Size

A total of 537 subjects will be randomized into one of three treatment groups, SUVN-502 (50 mg), SUVN-502 (100 mg) or placebo (179 subjects per group). With a sample size

of 537, there is at least 80% power to detect a 2-point drug-placebo difference on the ADAScog-11 with a standard deviation of 6, assuming a 2-sided 5% significance level and a drop-out rate of 20% or less.

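### The last covariance fallback, homogeneous compound symmetry with model-based errors, would understate the Week 26 standard error if the variance of change rises over time

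*SAP*

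**What the plan says.** SAP 4.7.2 tests each dose against placebo on change from baseline to Week 26 in ADAScog-11, using an MMRM with three post-baseline visits. The differences from "placebo will be reported for Weeks 4, 13, and 26". The within-subject matrix starts as unstructured. On non-convergence the order is "heterogeneous compound symmetry covariance structure and compound symmetry covariance structure, until the model converges".

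Degrees of freedom are Kenward-Roger. Neither the text nor the printed code asks for an empirical variance. Pooled site is a random effect at every step.

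SAP 4.7.3 applies the same model to the secondary endpoints, and SAP 4.4 repeats the analyses in the Evaluable Population. Protocol 8.5.1.2 names only an unstructured matrix and no fallback, so the sequence is an SAP addition.

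The only information on variability is in SAP 4.10 (and Protocol 8.9): a single value, "with a standard deviation of 6". There is no SD by visit and no between-visit correlation.

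**The concern.** An ordered, pre-specified fallback is good practice, and its first step is sound: heterogeneous compound symmetry keeps a separate variance for each visit. The last step does not. Homogeneous compound symmetry forces one variance on all three visits, while the hypothesis is about Week 26 alone.

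In a progressive disease the spread of change scores plausibly widens with follow-up. The pooled value would then sit below the Week 26 variance, and the Week 26 standard error and confidence interval would be too narrow. Kenward-Roger adjusts for having estimated the covariance parameters. It takes the chosen structure as correct and so does not repair this.

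At stake is the 5% level of the Week 26 test for any endpoint or subset whose fit reaches that step. Because SAP 4.7.1.3 makes no multiplicity adjustment, each comparison stands on its own 5% level.

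**Working it through.** **The plan's own figure.** Inputs from SAP 4.10: "2-point drug-placebo difference on the ADAScog-11 with a standard deviation of 6", two-sided 5%, at least 80% power, "a drop-out rate of 20% or less".

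- Normal approximation: n = 2 × (1.960 + 0.842)² × 6² / 2² = 141.3, so 142 per arm.
- Noncentral t: 142 gives 79.9% and 143 gives 80.2%, so 143 per arm.
- Allowing for dropout: 143 / 0.8 = 178.75, so 179 per arm, and 3 × 179 = 537.

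The stated sample size reproduces exactly. It supplies the two inputs used next: Week 26 SD 6 and 143 evaluable per arm.

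**Analytic check.** With complete data, the homogeneous structure estimates the common variance as the mean of the three visit variances. Hence:

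- true Week 26 SE = 6 × √(2/143) = 0.710
- ratio r = √(mean of the three variances / Week 26 variance)
- model SE = 0.710 × r
- actual two-sided type I error = 2 × [1 − Φ(1.96 × r)]

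Worked case, SDs 4/5/6: mean variance = (16 + 25 + 36)/3 = 25.67; r = √(25.67/36) = 0.844; model SE = 0.599; 1.96 × 0.844 = 1.655; type I error = 9.8%.

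All SDs at Weeks 4 and 13 are assumptions:

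| SD at Weeks 4/13/26 | Mean variance | r | Model SE | Type I error |
|---|---|---|---|---|
| 6/6/6 | 36.00 | 1.000 | 0.710 | 5.0% |
| 5.4/5.7/6 | 32.55 | 0.951 | 0.675 | 6.2% |
| 4.8/5.4/6 | 29.40 | 0.904 | 0.641 | 7.7% |
| 4/5/6 | 25.67 | 0.844 | 0.599 | 9.8% |
| 3/4.5/6 | 21.75 | 0.777 | 0.552 | 12.8% |
| 6.5/6.2/6 | 38.90 | 1.039 | 0.738 | 4.2% |

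**Simulation with dropout.** REML fits to 537 subjects in three arms, 20% random monotone dropout, assumed correlations of 0.6 between adjacent visits and 0.5 between Weeks 4 and 26, 400 trials with two comparisons each, Wald z tests, no site term.

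| SDs | Structure | Model SE | Empirical SE | Type I error |
|---|---|---|---|---|
| 4/5/6 | Unstructured | 0.689 | 0.694 | 4.4% |
| 4/5/6 | Heterogeneous CS | 0.692 | 0.695 | 4.4% |
| 4/5/6 | Homogeneous CS | 0.573 | 0.696 | 10.4% |
| 5/5.5/6 | Unstructured | 0.692 | 0.737 | 6.9% |
| 5/5.5/6 | Heterogeneous CS | 0.695 | 0.736 | 6.1% |
| 5/5.5/6 | Homogeneous CS | 0.629 | 0.736 | 9.4% |

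The 6.9% for the unstructured fit in the second scenario reflects simulation noise: the Monte Carlo error at a true 5% is about 0.8 to 1.1 percentage points. That scenario should be read by comparing structures within the same trials. In both scenarios only the homogeneous step has a clearly smaller model SE. The flat and falling cases were not simulated to completion and rest on the analytic result.

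**Convergence.** An unstructured matrix plus a random site intercept (60 pooled sites assumed) converged in 120 of 120 simulated full-size trials, 60 at site SD 0 and 60 at 0.5. The fit without site also converged in all 120. The site variance was estimated at zero in 45% and 27% of trials respectively. That is a boundary estimate and not a convergence failure. The optimiser was not PROC MIXED, and larger site SDs and small subsets were not tested.

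**Scope.** The calculation is for the Week 26 contrast that the SAP text names. The LSMEANS statement in the printed code has no week term and would give a contrast averaged over visits. With complete data that average would not have this bias.

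**The case against.** The main defence is that the SAP already contains the safeguard. Homogeneous compound symmetry is reached only if both the unstructured and the heterogeneous structures fail. With three visits the unstructured matrix has six parameters and about 500 subjects to estimate them. This stands, and it keeps the point minor.

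A second defence is that rising variance is assumed. This also stands. A reader might infer that the last step always understates the Week 26 standard error. The documents do not support that: they give one SD, and with equal or falling SDs the test is exact or conservative.

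A reader might also infer that the random site effect, spread over about 90 centres, is the likelier cause of non-convergence and should be dropped first. Nothing in either document says so, and the simulated fits did not show it. The model uses pooled sites with at least 2 subjects per treatment group (SAP 4.2.4), not raw centres. SAP 3.1 balances randomization by site, so keeping site in the model is defensible.

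Nor can it be said that the Evaluable Population or the subgroups will fit less well. Protocol 8.1.3 restricts the former to subjects who complete 26 weeks, which favours an unstructured fit, and the subgroup list in SAP 4.7.1.5 is redacted.

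Finally, SAP 4.11 allows changes after blinded review and before database lock. That gives a route to the correction, but it does not defend the step as written.

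**Conclusion.** The point holds in a limited, conditional form. If a fit reaches homogeneous compound symmetry and the Week 26 variance exceeds the three-visit average, the Week 26 test is anti-conservative. For assumed SDs from 5.4/5.7/6 to 3/4.5/6, the standard error is 5% to 22% too small (1 − 0.951 and 1 − 0.777). The analytic figures assume complete data and a Week 26 SD of 6. They are approximate for the SAP model, in which age, APO-E status and baseline MMSE do not interact with week.

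The intermediate heterogeneous step does not share the problem. The chance of reaching the last step in the primary mITT analysis is low, so the expected effect on the primary result is small. The sample size is unaffected. The case for acting is that the defect is confined to one step and is cheap to remove.

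**What to change.** In SAP 4.7.2, delete homogeneous compound symmetry as a model-based step. A workable order is:

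1. Unstructured, retried with other starting values.
2. Heterogeneous Toeplitz.
3. Heterogeneous compound symmetry.
4. Only if all of these fail, a simpler structure with an empirical (sandwich) variance and a compatible degrees-of-freedom method. The SAP should name that method and the clustering unit, since the model also carries a random site effect.

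The sandwich step should come last because it corrects the standard error and not the estimate. Under the missing-at-random assumption of SAP 4.7.1.2, the likelihood estimate itself relies on an adequate covariance model.

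The cost is a few lines of SAP text, with no change to data, conduct or sample size. If step 4 is used, Kenward-Roger degrees of freedom are lost. That matters little at about 143 per arm but more in small subsets, where sandwich errors are least reliable.

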4.7.3 Secondary Efficacy Endpoints

Secondary efficacy endpoints will be analyzed using the same MMRM model as for the primary efficacy endpoint (ADAScog-11). Changes from Baseline to Weeks 4, 13, and 26 in CDR-SB score, MMSE score, ADCS-ADL score, total NPI score, NPI distress score and C-SDD score will be assessed using the output from the MMRM analyses. Each secondary endpoint will be tested separately at $\alpha=0.05$ (2-sided).

Clinical Dementia Rating Scale – Sum of Boxes

The CDR is a global assessment of cognition and function rated in 6 domains: memory, orientation, judgment and problem solving, community affairs, home and hobbies, and personal care, which is used to assess the severity of dementia.

Each domain is rated on a 5-point scale of functioning as follows:

- 0: no impairment
- 0.5: questionable impairment
- 1: mild impairment
- 2: moderate impairment
- 3: severe impairment

Personal care is scored on a 4-point scale without a 0.5 rating available.

The CDR-SB score will be obtained by summing each of the domain box scores, with scores ranging from 0 to 18. Details of handling missing domains in the CDR-SB are summarized in [Section 4.7.1.2](#).

Summary

CDR-SB total scores will be summarized by treatment group and visit in terms of absolute values and changes from baseline, both for the observed case and LOCF analyses.

A plot showing the adjusted mean change from baseline in CDR-SB over time within each treatment group will be provided.

The homogeneity of the treatment effect for a number of important subgroups will be investigated as described in [Section 4.7.1.5](#).

A listing of subjects' observed and change from Baseline value will be provided.

Mini-Mental State Examination

The MMSE is a brief cognitive measure and assesses orientation to time and place, immediate and delayed recall of words, attention and calculation, language (naming, comprehension, and repetition), and spatial ability (copying a figure).

Subjects receive 1 point for each correct response to the questions. The total score is sum of the number of points awarded for each item, with a max score of 30.

Summary

MMSE scores will be summarized by treatment group and visit in terms of absolute values and changes from baseline, both for the observed case and LOCF analyses.

A plot showing the adjusted mean change from baseline in MMSE over time within each treatment group will be provided.

The homogeneity of the treatment effect for a number of important subgroups will be investigated as described in [Section 4.7.1.5](#).

A listing of subjects' observed and change from Baseline value will be provided.

Alzheimer's Disease Co-operative Study Activity of Daily Living

The ADCS-ADL is a validated scale for measuring functional abilities in activities of daily living in subjects with Alzheimer's disease. It measures 6 basic and 17 instrumental activities of daily living and was specifically developed as a sensitive tool to track changes in functional performance in Alzheimer's disease over time. The basic activities include self-care tasks such as eating, walking, toileting, bathing, grooming, and dressing. The instrumental activities are more complex skills that are required to successfully live independently and include shopping, keeping appointments, traveling outside of home, making a meal or snack, reading, and writing.

The ADCS-ADL has 23 questions and the total score is calculating by summing the scores of individual questions in the scale. Scores range from 0 to 78, with lower scores indicating greater impairment. Handling of missing items in the ADCS-ADL is summarized in [Section 4.7.1.2](#).

If a subject has 4 or more "don't know" responses at a particular visit, then the total score for that visit will be set to missing for the primary analysis. Exploratory analysis may be conducted that includes all scores regardless of the number of "don't know" responses.

Summary

ADCS-ADL scores will be summarized by treatment group and visit in terms of absolute values and changes from baseline, both for the observed case and LOCF analyses.

A plot showing the adjusted mean change from baseline in ADCS-ADL over time within each treatment group will be provided.

The homogeneity of the treatment effect for a number of important subgroups will be investigated as described in [Section 4.7.1.5](#).

A listing of subjects' observed and change from Baseline value will be provided.

Neuropsychiatric Inventory

The NPI is an interview-based tool for assessing behavioral domains common in dementia (delusions, hallucinations, agitation/aggression, depression/dysphoria, anxiety, elation/euphoria, apathy/indifference, disinhibition, irritability, aberrant motor behavior, sleep, appetite and eating disorders) in terms of frequency, severity, and caregiver distress.

Frequency is rated as:

1. Occasionally- less than once per week
2. Often- about once per week
3. Frequently- several times per week but less than every day
4. Very frequently- once or more per day

Severity is rated as:

1. Mild- produces little distress in the patient
2. Moderate- more disturbing to the patient but can be redirected by the caregiver
3. Marked- very disturbing to the patient and difficult to redirect

The score for each domain is: domain score = frequency x severity.

The Total NPI score is the sum of each domain. There are 12 items in the NPI, so the maximum score is 144 (12 for each domain).

NPI subtotals will be based on the following:

- NPI Domains: Delusions + Hallucinations will sum the delusions and hallucinations domains. The maximum score is 24.

- [REDACTED]
- [REDACTED]
- [REDACTED]
- [REDACTED]
- [REDACTED]

Additionally, the total distress score for the NPI is the sum of the scores of the individual caregiver distress questions.

Caregiver distress is scored as:

0. Not at all
1. Minimally
2. Mildly
3. Moderately
4. Severely
5. Very severely or extremely

The maximum score is 60 (5 for each domain) for the total caregiver distress score.

Summary

Total NPI scores and NPI distress scores will be summarized by treatment group and visit in terms of absolute values and changes from baseline, both for the observed case and LOCF analyses.

A plot showing the adjusted mean change from baseline in the total NPI score and NPI distress score over time within each treatment group will be provided.

NPI domain scores will also be summarized individually using the same methods as the NPI total score.

The homogeneity of the treatment effect for a number of important subgroups will be investigated as described in [Section 4.7.1.5](#).

Additional NPI domain and subtotal analyses will be performed on subsets of the mITT Population and EP:

- [REDACTED]
- [REDACTED]

A listing of subjects' observed and change from Baseline value will be provided.

Cornell Scale for Depression and Dementia

The C-SDD was specifically developed to assess signs and symptoms of major depression in demented subjects.

The scale contains nineteen questions, divided into 5 sub-scales, with each question given a score ranging from 0 (absent) to 2 (severe):

- Mood-related signs: anxiety, sadness, a minimal reaction to pleasant events and irritability
- Behavioral disturbance: agitation, psychomotor retardation, multiple physical complaints and loss of interest
- Physical signs: loss of appetite, weight loss and lack of energy
- Cyclic functions: diurnal variation in mood, difficulty falling asleep, multiple awakening during the night and early morning awakening
- Ideational disturbance: suicidal tendencies, low self-esteem, pessimism and mood-congruent delusions

The total score for the C-SDD is the sum of each item in each section labeled "rater's opinion." The maximum score for this scale is 38. If the question is marked 'unable to evaluate' on the eCRF, the response will be replaced with a score of 0. However, the

score will only be calculated if there are at most 20% of the C-SDD items (3 out of 19) with the rating “unable to evaluate.” Otherwise, the total score will be missing.

Summary

C-SDD scores will be summarized by treatment group and visit in terms of absolute values and changes from baseline, both for the observed case and LOCF analyses. If the range of total scores is less than ten, an additional decimal place will be added to the continuous summaries. Otherwise, 1 decimal place will be used.

A plot showing the adjusted mean change from baseline in C-SDD over time within each treatment group will be provided.

A listing of subjects’ observed and change from Baseline value will be provided.

